11.4.2.4 Assessment of Knee Stability

The side-to-side difference of the KT-1000 Arthrometer Test will be reported in group mean and standard deviation. The two group means will be compared with the Mann-Whitney U test. The side-to-side difference [86] scores of the Lachman Test and the Pivot Shift Test will be reported in frequencies. Statistical inference testing will be done using the Mann-Whitney U test.

11.4.2.5 Tegner Activity Scale

The difference in TAS scores from baseline (pre-injury state) to follow-up will be reported in group mean and standard deviation. The two groups will be compared using the Mann-Whitney U test.

11.4.3 Other Outcomes of Interest

11.4.3.1 Intra-Patient Comparison of Ossification

The within-subject differences in femoral vs. tibial relative change in bone tunnel volume will be assessed for the interventional patient group. For descriptive statistics, mean and standard deviation values will be reported. For statistical inference testing, the null hypothesis in this setup is a mean difference in femoral vs. tibial relative change in bone tunnel volume equal to zero. If the normality assumption holds (Kolmogorov-Smirnov Test), a paired t test is applied to test for a significant two-sided departure from zero. Otherwise, a Wilcoxon signed-rank test will be used.

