5 STUDY OUTCOMES

5.1 Primary Outcome

The primary outcome variable of this study is the relative change of the CT evaluated femoral bone tunnel volume from baseline to follow-up at 12 months.

As the primary objective of the use of the OCS is to reduce tunnel widening by promoting bony ingrowth into the bone tunnel, the relative change of bone tunnel volume over time is an appropriate measure to quantitatively assess this effect. Assessing relative changes as opposed to absolute values negates the potential for bias by different tunnel drill sizes used in the two treatment arms potentially influencing the absolute ossification/de-ossification. In quantifying bone tunnel size, CT measurements provide substantially more reliable means than plain radiography or magnetic resonance imaging [50, 68].

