5.3.3 Intra-Patient Comparison of Ossification

The intervention group will be additionally assessed in an intra-patient comparison model [51]. Using the available CT data, the tibial bone tunnel volume will be calculated using the same method as for the femoral bone tunnel volume described below. The relative change of the two parameters will be compared.

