8.1 Femoral Fixation Construct

Control Group: Doubled suture loop (Ethibond 6) at appropriate length determined intra-operatively connected to the femoral cortical fixation button (FlippTack, Karl Storz).

Intervention Group: Doubled suture loop (Ethibond 6) at appropriate length determined intra-operatively connected to the femoral cortical fixation button (FlippTack, Karl Storz). This construct is additionally connected to the device under study according to the interventional surgical technique guide.

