8.3 Bone Tunnels

The harvested unsutured tendon-graft must measure between 8 and 8.5 mm in diameter at the end to be inserted into the femoral bone tunnel for subject inclusion (see chapter 7.1.2). Enlacing the OCS increases the graft diameter by 1 mm (Determined experimentally).

Accordingly, the overdrilled socket of the femoral bone tunnel has the following diameter depending on the subject's group assignment:

- Intervention group: 9 - 9.5 mm
- Control group: 8 – 8.5 mm

The tibial bone tunnel is drilled at a diameter of 8 ± 1 mm as applicable.

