8.4 Surgical Technique

The surgical technique under study uses a semitendinosus tendon autograft (combined with gracilis tendon if applicable) harvested from the index knee or the contralateral knee according to the standard in-house technique. The pes anserinus is visualized through a three centimeter incision anteromedially at the proximal tibia. The semitendinosus tendon is harvested with a tendon stripper and length and thickness is measured. For the intraarticular procedure, standard medial and lateral parapatellar arthroscopy portals are used. After overdrilling with a 4.5 mm drill, the final femoral graft tunnel is created by a cannulated drill. Afterwards the tibial tunnel is prepared by using a drillguide (Karl Storz, Tuttlingen, Germany) targeted at the center of the tibial ACL footprint. The tendon graft is inserted first into the femoral bone tunnel through the medial portal. In the femoral tunnel the graft is secured using a flipping device on the cortical bone (Flipptack, KarlStorz, Tuttlingen, Germany). Tibial graft-fixation is achieved using an interference screw (Megafix, Karl Storz, Tuttlingen, Germany) proximally, and a small plate (Endotack, Karl Storz, Tuttlingen, Germany) covering the bone tunnel distally.

The table below shows a schematic of the surgical techniques for graft fixation under study and the material in use.

Control Intervention	Experimental Intervention

1) Femoral cortical fixation: Flipptack (Karl Storz) 2) Femoral Graft suspension: Ethibond 6 (Ethicon Inc.) Suture bone tunnel; diameter: 4.5 mm 3) Cannulated bone tunnel; diameter: 8 – 8.5 mm Length: 27 mm 4) Tendon graft 5) Resorbable interference screw fixation (Megafix, Karl Storz) 6) Tibial bone tunnel; Diameter: 8 – 8.5 mm Tibial Graft suspension: Fibre Wire 2 (Ethicon Inc.) and Ethibond 6 7) Tibial cortical fixation: Endotack (Karl Storz)
	
1) Femoral cortical fixation: Flipptack (Karl Storz) 2) Femoral Graft suspension: Ethibond 6 (Ethicon Inc.) Suture bone tunnel; diameter: 4.5 mm 3) Cannulated bone tunnel; diameter: 9 – 9.5 mm Length: 27 mm 4) Tendon graft 5) Resorbable interference screw fixation (Megafix, Karl Storz) 6) Tibial bone tunnel; Diameter: 8 – 8.5 mm Tibial Graft suspension: Fibre Wire 2 (Ethicon Inc.) and Ethibond 6 7) Tibial cortical fixation: Endotack (Karl Storz) Black Arrow: Medical device under study enlaced into tendon graft.

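### The femur-versus-tibia test is run against zero in the intervention arm only, so its result cannot be attributed to the scaffold in either direction

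*Combined protocol and SAP*

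**What the plan says.** Section 5.3.3, under other outcomes of interest, states: "The intervention group will be additionally assessed in an intra-patient comparison model". On the data source it says: "Using the available CT data, the tibial bone tunnel volume will be calculated", by the method used for the femur. Section 11.4.3.1 gives the analysis: "The within-subject differences in femoral vs. tibial relative change in bone tunnel volume will be assessed for the interventional patient group". The null is a mean femoral-tibial difference of zero, tested two-sided by a paired t test, or by a Wilcoxon signed-rank test if normality fails. No counterpart is planned for controls.

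The surgical sections describe two different tunnels.

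- Femur (section 8.4): "In the femoral tunnel the graft is secured using a flipping device on the cortical bone".
- Tibia (section 8.4): "Tibial graft-fixation is achieved using an interference screw" proximally, with a small plate distally.
- Scaffold: it is placed only in the femoral tunnel of intervention patients. After describing the same button and suture loop as in controls, section 8.1 adds: "This construct is additionally connected to the device under study according to the interventional surgical technique guide".
- Drill diameter: the femoral socket is 9-9.5 mm in the intervention arm and 8-8.5 mm in controls (section 8.3). For the tibia, section 8.3 says: "The tibial bone tunnel is drilled at a diameter of 8 ± 1 mm as applicable", while the table in section 8.4 gives 8-8.5 mm in both arms.

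**The concern.** The tibia serves as the scaffold-free reference within each intervention patient. That works only if the two tunnels would change equally without the scaffold, and nothing in the documents supports this. Section 3.1.1 points the other way. It reports that interference-screw material alters tunnel widening, and that one composite screw reduced widening in the tibia but not in the femur. Fixation and site can therefore affect this outcome by the protocol's own account.

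Controls have the same femoral button and the same tibial screw and plate without the scaffold, so they could show how far the tunnels diverge for other reasons. The plan does not use them for this. At stake is the interpretation of a p-value that section 13 would carry into publication with the full data analysis. A reader would naturally credit a significant result to the device, or take a null result as evidence against it.

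**Working it through.** **Plan's own figure.** Section 11.2 uses a difference of 20 points, SD 25.175, two-sided alpha 0.05 and power 0.80. By the normal approximation, n per group = 2 × (1.960 + 0.842)² × (25.175/20)² = 24.9, so 25. Then 50/0.9 = 55.6, so 56. Both figures reproduce. By the exact noncentral t, power at 25 per group is 0.786. No size or power is stated for the femur-tibia test.

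**Inputs and assumptions.** n = 25 and SD 25.175 come from section 11.2. These are assumed because the documents do not give them:

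- the same SD for the tibial tunnel;
- a femur-tibia correlation (rho) of 0, 0.3 or 0.5;
- a scaffold-unrelated gap of 5, 10 or 15 points;
- alpha 0.05 for the paired test (section 11.4 sets 0.05 for between-group tests only).

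**Step 1. SD of the within-patient difference** = 25.175 × √(2(1 − rho)) = 35.6, 29.8 and 25.2 for rho = 0, 0.3 and 0.5.

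**Step 2. One-arm paired t test as planned.** Noncentrality = net difference × √25 / SD of difference, with 24 degrees of freedom. The net difference is the scaffold effect plus the unrelated gap.

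| Net difference (points) | rho 0 | rho 0.3 | rho 0.5 |
|---|---|---|---|
| 5 | 0.104 | 0.127 | 0.159 |
| 10 | 0.271 | 0.364 | 0.479 |
| 15 | 0.525 | 0.676 | 0.815 |
| 20 | 0.769 | 0.896 | 0.968 |

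- *Inert scaffold.* The net difference is the gap itself, so gaps of 5, 10 and 15 points give significance in 10-16%, 27-48% and 53-82% of trials. These are rejection rates, not type I error, because the literal null is then false.
- *True 20-point scaffold effect.* With no gap, power is 77-97%. An opposing gap of 10 leaves a net 10, and power is 27-48%. An opposing gap of 15 leaves a net 5, and power is 10-16%.

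**Step 3. Between-arm contrast of the same difference** (two-sample t, 25 per arm). A gap common to both arms cancels, so with no scaffold effect and no other arm difference the rejection rate is 0.05 whatever that gap is. 95% CI half-width = t(48) × SD of difference × √(2/25), with t(48) = 2.011.

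| | rho 0 | rho 0.3 | rho 0.5 | Primary femoral contrast |
|---|---|---|---|---|
| Power for 20 points | 0.495 | 0.643 | 0.786 | 0.786 |
| CI half-width (points) | 20.2 | 16.9 | 14.3 | 14.3 |

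**Step 4. What the contrast does not remove.** The arms differ in femoral drill diameter. Section 5.1 says: "Assessing relative changes as opposed to absolute values negates the potential for bias by different tunnel drill sizes used in the two treatment arms". That is so if enlargement is proportional. If instead every tunnel, taken as a uniform cylinder, gained 1 mm in diameter, the relative volume change would be ((d + 1)/d)² − 1:

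- 8 mm: 26.6%
- 8.5 mm: 24.9%
- 9 mm: 23.5%
- 9.5 mm: 22.2%

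The arm difference is then 26.6 − 23.5 = 3.1 or 24.9 − 22.2 = 2.7 points, about 3.

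**The case against.** The documents never say that rejecting the null would show a scaffold effect. They say only that the two changes are compared, and for that literal question the test is sound. The scaffold question belongs to the randomised femoral comparison. The femur-tibia item is absent from the hypothesis, the power table and the stopping rule. The gap sizes and correlations above are hypothetical. Section 3.1.1 gives widening incidences of 25-100% for the femur and 29-100% for the tibia, which show no clear gap. The between-arm contrast also costs extra segmentation for no more precision than the primary analysis over the range shown.

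Much of this stands. The item is not confirmatory, the percentages are only an illustration, and the contrast can only be supportive. The precision comparison depends on equal SDs. In general the contrast gains power over the primary only if rho exceeds SD(tibia)/(2 × SD(femur)). With a femoral SD of 25.175, an assumed tibial SD of 15 puts that threshold at about 0.30, and an SD of 35 at about 0.70. With equal SDs and rho = 0.7, power would be 0.94.

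The objection does not rescue the planned inference. The tibia has no evident purpose here other than as a scaffold-free reference, and the incidence ranges do not show that the gap in volume change is zero.

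**Conclusion.** The concern holds, at minor severity. The planned p-value answers whether the two tunnels change differently in intervention patients. It does not isolate the scaffold, because fixation always differs between the tunnels and drill diameter usually does (the stated ranges can meet at 9 mm). A significant result does not show a scaffold effect, and a non-significant one does not exclude it.

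This conclusion rests on the documents' description of the surgery and not on the illustrative rejection rates, which depend on an assumed gap, correlation and tibial SD. The size and direction of any real gap are unknown.

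**What to change.** In sections 5.3.3 and 11.4.3.1, compute the femur-minus-tibia difference in relative volume change in both arms. Report the between-arm difference with a 95% CI as exploratory, and keep the within-intervention result as description only. First confirm that control scans cover the tibial tunnel.

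State two limits in the text:

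1. The contrast removes only gaps common to both arms. The arm difference in femoral drill diameter remains.
2. It supports and does not replace the primary femoral comparison. With equal tunnel SDs it is no more powerful than the primary unless the correlation exceeds 0.5.

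The two tibial diameter ranges in sections 8.3 and 8.4 should also be reconciled.

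**Cost.** CT is already scheduled for every patient at Visits 2, 4 and 5, so no new imaging is needed if coverage is confirmed. The work is tibial segmentation of up to 28 × 3 = 84 control scans, or 28 × 2 = 56 if limited to baseline and Visit 5, plus the SAP wording. Precision will be modest.

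If this is not done, one sentence in section 11.4.3.1 should label the analysis descriptive and non-causal. That avoids the misreading but does not make the comparison informative about the scaffold.

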11.4.4 Plain Radiography assessed Bone Tunnel Widening

Radiographically assessed relative change of femoral bone tunnel width will be reported in group-mean values and in group standard deviation. Inter-group comparison will be performed using Student's t-test based on the relative change of femoral bone tunnel width at each assessed time point.

11.4.5 Interim analysis

An interim analysis will be conducted when the first 10 interventional patients have reached 4.5 months follow-up (Visit 4). All available data will be assessed, analyzed and evaluated equivalently to the full data analysis. To mitigate the risk for type II error, stopping criteria only include the primary outcome variable. Statistically significant ($P \leq 0.05$) inferiority of the interventional treatment in the primary outcome variable will lead to premature termination of the trial.

11.4.6 Safety Analysis

Safety will be evaluated by tabulations of AE's and SAE's and will be presented with descriptive statistics at baseline and follow-up visits for each treatment group. Inferential analyses of (serious) adverse events are not done.

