9.2.5 Assessment of Safety Outcomes

9.2.5.1 Adverse Events

Intra-operative complications (if any) will be recorded on the eCRF. Self-reported AEs will be assessed by interviewing the patient. The following question will be used:

“Hatten Sie im Zusammenhang mit Ihrer Knieoperation irgendwelche nennenswerten medizinischen Probleme?”

Also any out of window visit or unexpected finding will be recorded. The following adverse event information will be recorded:

- Adverse event term
- Date of onset
- Date of resolution/Duration
- Severity (Subjective assessment by PI)
- Seriousness
- Relationship with surgical intervention
- Relationship with device under study
- Actions taken in response
- Outcome of the adverse event

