9.3.2.2 Preoperative Clinical Examination

Clinical examination will be conducted by the PI. The following information will be recorded in the eCRF:

- Date of examination.
- Intra/Extra-articular effusion.

- Knee mobility.
- Anterior displacement of the affected and of the healthy knee using the Lachman Test and the KT-1000 Arthrometer Test.
- Online survey for all patient-completed questionnaires (IKDC SKEF, LKSS and TAS)
- Rotational stability of both knees using the Pivot shift test.

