9.3.3 Follow-up 1 (Visit 3)

Follow-up 1 will be performed 42 days after surgery. The patient will be asked to fill an online survey for all patient-completed questionnaires (IKDC SKEF, LKSS and TAS) in the clinic. Subsequently, the clinical examination is conducted by the PI recording the identical points as during the preoperative clinical examination and the occurrence of any potential AEs. Plain radiography measurement is performed according to ACLROCS_WI_PlainRadiography.

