10 SAFETY

10.1 Medical Device Category A studies

10.1.1 Definition and Assessment of safety related events

Adverse Event (AE)

Any untoward medical occurrence, unintended disease or injury or any untoward clinical signs (including an abnormal laboratory finding) in participants, users or other persons whether or not related to the investigational medical device [ISO 14155: 3.2].

Serious Adverse Event (SAE)

Adverse event that:

- results in death, or
- led to a serious deterioration in health that either:
 - results in a life-threatening illness or injury, or
 - results in a permanent impairment of a body structure or a body function, or
 - required in-patient or prolonged hospitalisation, or
 - results in medical or surgical intervention to prevent life threatening illness, or
- led to fetal distress, death or a congenital abnormality or birth defect. [ISO 14155: 3.37].

Health hazards that require measures

Findings that may require additional action are:

- Persistent anterior knee pain
- Septic arthritis
- Arthrofibrosis
- Graft rupture
- Aseptic effusion
- Subcutaneous cyst

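### Effusion and knee mobility are examined at Visits 2 to 7 but no outcome or analysis uses them, so by-arm counts of two named hazards depend on how the investigator codes adverse events

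*Combined protocol and SAP*

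**What the plan says.** **Collection.** Section 9.3.2.2 has the investigator record, among other items, "Intra/Extra-articular effusion" and "Knee mobility" in the eCRF before surgery. No grading scale, unit or threshold is given for either. At follow-up 1, section 9.3.3 says that "the clinical examination is conducted by the PI recording the identical points as during the preoperative clinical examination", and in the same sentence has adverse events recorded. Sections 9.3.4 to 9.3.7 carry the examination forward to Visits 4 to 7. The study schedule marks clinical examination at Visits 2 to 7 and not at screening.

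**Named hazards.** Section 10.1.1 lists "Aseptic effusion" and "Arthrofibrosis" among the findings that could call for further action.

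**Route into the safety data.** Section 9.2.5.1 collects adverse events from intra-operative complications and one open interview question to the patient, and adds that "any out of window visit or unexpected finding will be recorded". Severity is the investigator's subjective assessment.

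**Analysis.** Section 4.4 aims to describe how often complications occur and how severe they are. Section 11.4.6 reads "Safety will be evaluated by tabulations of AE's and SAE's", presented descriptively by visit and treatment group, with no inferential analysis.

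**The concern.** Two items are scheduled for every patient at six visits, in both arms, and bear on hazards that the protocol itself names. The analysis plan never summarises them. What the report will show about effusion and loss of motion is the subset of findings that became adverse event entries.

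The step from finding to entry has no stated rule. The person who examines the knee also records the adverse events and grades them, and section 6.3.2 describes the trial as patient-blinded without declaring this examiner blinded. The by-arm counts therefore mix how often the finding occurred with how readily it was coded, and a reader of the report could not separate the two. At stake is the safety statement promised in section 4.4, not the primary comparison of tunnel volume.

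**Working it through.** **1. Trace the two items through the plan.**

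| Place | Effusion | Knee mobility |
|---|---|---|
| Examination, Visit 2 (9.3.2.2) | recorded | recorded |
| Examination, Visits 3 to 7 (9.3.3 to 9.3.7) | recorded again | recorded again |
| Related finding in 10.1.1 | aseptic effusion | arthrofibrosis |
| Primary outcome (5.1) | no | no |
| Secondary outcomes (5.2) | no | no |
| Other outcomes (5.3) | no | no |
| Safety outcomes (5.4) | only as an adverse event | only as an adverse event |
| Analyses (11.4.2 to 11.4.5) | none | none |
| Safety analysis (11.4.6) | only as an adverse event | only as an adverse event |

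The analyses in section 11.4 cover tunnel volume, IKDC, Lysholm, KT-1000, Lachman, pivot shift, Tegner, femoral versus tibial tunnel volume, radiographic tunnel width, and adverse event tables. The interim analysis (11.4.5) takes in all available data, but in the manner of the full analysis, which has no rule for these two items.

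**2. Look for a rule that links a finding to an adverse event.** Section 10.1.1 defines adverse events broadly enough to include clinical signs. Section 9.3.3 has adverse events recorded at the examination. Section 9.2.5.1 adds unexpected findings but does not define them. No section says what degree or duration of effusion or motion loss is entered. Entry is permitted, and when it happens is left open.

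**3. How many patients.** Inputs from section 11.2: difference 20%, standard deviation 25.175%, two-sided alpha 0.05, power 0.8, drop-out 10%.
- n per group = 2 × (1.960 + 0.842)² × (25.175/20)² = 24.9, so 25, as stated. A t-based calculation gives 25.87, so 26; this does not matter here.
- 25/0.9 = 27.8, so 28 per arm and 56 in total, as stated.

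**4. What 28 per arm means for a count.** The documents give no rate for either finding, so the rates below are assumptions shown as a range.
- One finding coded or not coded shifts an arm's proportion by 1/28 = 3.6 points; three shift it by 3/28 = 10.7 points.
- Chance of at least one case in an arm, 1 − (1 − p)²⁸: 43% at p = 2%, 76% at 5%, 95% at 10%.
- If an arm has no case, the one-sided 95% upper limit is 1 − 0.05^(1/28) = 10%.
- Widest 95% half-width for a difference in proportions (both at 50%): 1.96 × √(2 × 0.25/28) = 26 points; with 25 per arm, 1.96 × √(2 × 0.25/25) = 28 points.

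A few coding decisions can thus visibly change an adverse event table of this size. Tables of the examination data will be imprecise too, but will not depend on that coding step.

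**The case against.** **The adverse event system already covers these findings.** In large part it does. A reader might infer that an effusion seen on examination can be counted only if the patient complains or the examiner finds it unexpected. The documents do not support that: the definition in 10.1.1 includes clinical signs whether or not device-related, and adverse events are recorded at the examination itself. Section 11.4.6 also already tabulates by visit and arm. What stands is narrower: no rule for entry, and no display of what was examined. Reporting to the ethics committee within 2 days (10.1.2) concerns hazards that require measures and is not a comparison by arm.

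**The examination has the same unblinded examiner.** True. Using the examination data removes the coding step, not the examiner's knowledge of the arm. The patient-reported swelling item in the Lysholm scale is systematic and comes from a blinded patient, but it is worth 10 of 100 points and is analysed only within the total.

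**A hidden excess in the scaffold arm.** A reader might infer that persistent effusion is the expected sign of a reaction to the scaffold, and that differential coding would conceal it. The documents do not say so: section 3.6.2 anticipates cysts, and no event or coding rates are given. Even an assumed 30% versus 10% with 28 per arm gives 20 points with a half-width of 1.96 × √(0.3 × 0.7/28 + 0.1 × 0.9/28) = 20.3 points, an interval that includes zero.

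**The data may be neither complete nor in the needed format.** This stands. Drop-out is planned for, rerupture leads to withdrawal (7.4), and section 8.8 excludes patients with complications during surgery with the product from further analysis. An examined effusion is also not the same as aseptic effusion, nor reduced mobility the same as arthrofibrosis.

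**Conclusion.** The gap holds in a limited form. Effusion and knee mobility are systematically scheduled at Visits 2 to 7, relate to two findings named in 10.1.1, and appear in no outcome and no analysis except through adverse event entries. Because no rule governs entry and the investigator is not declared blinded, the by-arm counts for these hazards depend on coding judgement.

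The documents do not show that harms would be missed, that coding would differ between arms, or in which direction. The size of any distortion is therefore unknown; the only firm figure is the 3.6-point step per patient at 28 per arm, slightly larger with fewer examined. The link from the examination items to the named hazards is a clinical inference, though a close one. The change is worth making because the data are already planned and the safety objective asks for frequency. It has no bearing on the primary conclusion.

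**What to change.** Add to section 11.4.6:

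1. Descriptive tables of effusion and of knee mobility by arm at each of Visits 2 to 7, in the form recorded on the eCRF, in all randomised patients examined, with the number examined at each visit.
2. Between-arm differences with 95% confidence intervals. For mobility, adjust the difference for the preoperative value only if mobility is recorded numerically.
3. A cross-tabulation of these findings against adverse event entries, by arm, so that findings not entered are visible.
4. A statement that these are descriptive safety estimates without hypothesis tests, in keeping with the rest of the section.

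The sponsor should also say whether a rule exists for when an examination finding is entered as an adverse event, and state it if so. Setting such a rule is the sponsor's clinical decision.

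The cost is SAP wording and a few tables from data already planned for the eCRF, with no new measurement or staff. The downside is a few more estimates with wide intervals, at about 28 per arm or fewer.
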